3.2 Study equipment

A standard adult manikin will be used in scenarios. CPR quality will be measured using a CPRmeter device (Laerdal Medical, Stavanger, Norway), or similar accelerometer-based CPR measurement device. Any device visual or audio CPR quality feedback will be disabled during the scenario. Data will be extracted using manufacturer software.

4. ADVERSE EVENT MANAGEMENT

4.1 Definitions

4.1.1 Adverse Events (AE)

An AE is: “Any untoward medical occurrence in a patient or clinical investigation participant taking part in health care research, which does not necessarily have a causal relationship with the research”.

The reporting periods for adverse events is from the time of written consent to completion of the CPR quality assessment. All adverse events that occur between these time-points should be recorded in the case report form.

In view of the nature of the trial, adverse events should only be recorded if the event may be associated with study participation.

4.1.2 Serious Adverse Events (SAEs)

A Serious Adverse Event is a recordable AE that fulfils one or more of the following criteria:

- Results in death
- Is immediately life-threatening
- Requires hospitalisation or prolongation of existing hospitalisation

- Results in persistent or significant disability or incapacity
- Is a congenital abnormality or birth defect
- Is an important medical condition.

4.2 Reporting SAEs

All **SAEs** occurring from the time of **written informed consent** until the completion of the CPR quality assessment must be recorded on the study Searios Adverse Event Form and faxed to the Sponsor **within 24 hours** of the research staff becoming aware of the event.

For each **SAE** the following information will be collected:

- full details of the event,
- event duration (start and end dates, if applicable),
- action taken,
- outcome,
- seriousness criteria,
- causality (i.e. relatedness to intervention), and,
- whether the event would be considered expected or unexpected.

Any change of condition or other follow-up information should be faxed to the Sponsor as soon as it is available or at least within 24 hours of the information becoming available. Events will be followed up until the event has resolved or a final outcome has been reached.

SAEs will be reported using the SAE form in the participant's CRF. The Principal Investigator in each centre must report any SAEs to the study sponsor within 24 hours of them becoming aware of the event. The SAE form should be completed and faxed to the dedicated fax at Heart of England NHS Foundation Trust. The trial team will liaise with the investigator to compile all the necessary information. The trial coordinating centre is responsible for reporting any related and unexpected SAEs to the sponsor and REC within required timelines.

The principal investigator at the research site is responsible for the recording of AEs and reporting of SAEs in line with the requirements of the protocol.

5. DATA MANAGEMENT

Personal data collected during the trial will be handled and stored in accordance with the 1998 Data Protection Act.

Participants will be identified using a unique trial number and their initials. Details of the management of personal data will be described in the participant information sheet.

5.1 Data collection and management

Case Report Forms (CRFs) will be developed to collect all required trial data.

Demographic data will be recorded at the time of consent through direct questioning of the participant by research staff by a member of research staff.

CPR quality assessment will be collected using a CPR quality measurement device (see section 3.2).

5.2 Database

A trial database will be developed, which will be used to store inputted study data.

5.3 Data storage

All essential documentation and trial records will be stored by Heart of England NHS Foundation Trust in accordance with local policy. Access to stored information will be restricted to authorised personnel.

5.4 Data access and quality assurance

Participant data will be recorded in an anonymised format by referring to participants as initials and participant number. Personal information will be retained with explicit consent, only for the purpose of sending out study results (if requested by the participant) or to send out details of CPR training, which will be offered to participants. Personal identifiable information will be stored separately to study results.

A screening log will be used to capture anonymised details of the number of people approached to participate and reasons for people not participating in the study, based on the exclusion criteria.

Study data will be stored securely. Written records will be stored in locked offices, accessible only to study personnel. Electronic data will be stored on password protected computers accessible only to study personnel.

5.5 Archiving

Trial documentation and data will be archived for at least ten years after completion of the trial, in accordance with sponsor policy.

6. STATISTICAL ANALYSIS

6.1 Power and sample size

We will recruit a total of 330 participants. We require 102 participants in each study arm to reliably detect a 5 mm difference in chest compression depth between groups with 90% power and a

significance level of 0.05. In making this sample size calculation, we have made a conservative estimate of the standard deviation (11), as described in the study by Mirza et al.[20] The difference of 5mm is considered clinically important based on large observational studies of the association between chest compression depth and survival following OHCA.[5, 6, 13]

We have included an additional 24 participants to account for drop-outs and data loss.

6.2 Statistical analysis of efficacy and harms

6.2.1 Statistics and data analysis

Data will be analysed using SPSS statistical software.

Continuous data will be assessed for normality. Normally distributed continuous will be described as mean and 95% confidence, Non-normally distributed continuous data will be described as median and interquartile range. Categorical data will be described as number and percentage.

Baseline demographics for each treatment group will be reported using descriptive statistics.

For the analysis of outcomes, we will conduct two groups of analyses:

1. The first analysis will compare each of the outcomes with another outcome (i.e. “at least” v “approximately”; “approximately” v “hard and fast”; “hard and fast” v “at least”). For continuous data, we will report the mean difference, 95% confidence interval, and p-value (t-test). For dichotomous outcomes, we will report the odds ratio, 95% confidence interval, and p-value (chi-squared test or similar).
2. The second analysis will compare all three groups, using an ANOVA test, Kruskal-Wallis test, or Chi-square test, depending on the type of data.

All analyses will be on an intention-to-treat basis. We do not plan to undertake any adjusted analyses. All tests will be two-tailed with a p-value cut-off for significance of 0.05.

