2.3.1 Primary efficacy outcomes

The primary outcome is mean chest compression depth measured during the CPR quality assessment.

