2.8 Trial treatments / intervention

2.8.1 Trial treatment(s) / intervention

Randomisation and the CPR quality assessment will take place as soon as possible after written informed consent has been obtained.

The CPR quality assessment will consist of a simulated cardiac arrest. On entering the simulation area, participants will be presented with a standardised scenario. They will be informed that they have entered a room at their local community centre and found a 70-year old male collapsed on the floor. They will be informed that they have phoned 999 and provided the location of the event and that the ambulance is en-route. The 999 operator will then guide the participant as to how to commence CPR using a standardised script. We will use a standardised script, based on that used by UK Ambulance Services to direct the dispatcher-assisted CPR. The only difference between the scripts will be the wording to describe the target chest compression depth. All participants will be directed to deliver compression-only CPR.

The instructions will be delivered using a pre-recorded audio recording. The participant will not have the opportunity to ask questions. If a question is asked, the researcher in the room will respond that the participant should follow the instructions on the audio recording

Each participant will deliver chest compressions for approximately two minutes following the delivery of the first chest compression.

After the scenario, the researcher will provide feedback on the participant's performance, based on their subjective assessment of performance.

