3. METHODS AND ASSESSMENTS

3.1 Schedule of delivery of intervention and data collection

The schedule of delivery of the intervention and data collection is detailed in table one.

Table 2: Schedule of events

Visit	1	2
Visit Window		Immediately after randomisation
Informed consent	✓	
Inclusion/exclusion criteria	✓	
Demographic information*	✓	
CPR quality assessment		✓
Adverse events	✓	✓
*- Demographic information will include key variables, such as age, gender, height, weight, previous CPR training, previous resuscitation use.		

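### The plan rules out every adjusted analysis although likely predictors of compression depth are recorded before randomisation; this is valid but forgoes likely precision on the primary outcome

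*Protocol*

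**What the plan says.** Protocol section 2.3.1 sets the endpoint: "The primary outcome is mean chest compression depth measured during the CPR quality assessment". Section 6.2.1 compares the arms pairwise ("For continuous data, we will report the mean difference, 95% confidence interval, and p-value (t-test") and all together by ANOVA or an equivalent. It then closes the door on covariates for every outcome: "We do not plan to undertake any adjusted analyses". No reason is given.

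The footnote to the schedule of events in section 3.1 lists what is collected at visit 1: "Demographic information will include key variables, such as age, gender, height, weight, previous CPR training, previous resuscitation use". Section 5.1 fixes the timing ("Demographic data will be recorded at the time of consent") and section 2.8.1 puts allocation after that ("Randomisation and the CPR quality assessment will take place as soon as possible after written informed consent has been obtained"). The only stated use of these data is descriptive: "Baseline demographics for each treatment group will be reported using descriptive statistics".

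Section 6.1 sizes the trial for a raw two-group difference: "We require 102 participants in each study arm to reliably detect a 5 mm difference in chest compression depth between groups", with 90% power, a significance level of 0.05 and an SD of 11. Section 2.7.1 gives 1:1:1 individual randomisation by an internet-based system and names no stratification factor.

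**The concern.** The outcome is two minutes of physical work done kneeling, which section 1.6 says some people may find tiring. Eligibility is wide: adults over 18 drawn from non-clinical staff, outpatients and visitors. Only practical CPR training within the last two years is excluded, so older training will vary between participants. Age, gender, body size and training history are therefore plausible sources of the between-person spread that determines the sample size.

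Because these variables are collected anyway, leaving them out of the model saves no data collection. Adjusting for them would remove the part of the variance they explain and would account for chance differences between arms. The protocol makes an explicit decision against this, so the matter has not simply been left to a statistical analysis plan. If adjustment were added after the data were seen, it would contradict the protocol and could look data-driven. What is at stake is the width of the intervals and some power on the primary outcome, not the validity of the comparison.

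**Working it through.** **Inputs from the protocol.** Difference 5 mm, SD 11, 102 per arm, 24 added for losses, total 330 (section 6.1); two-sided 0.05 (section 6.2.1); arm SDs of 11.6 and 10.2 in the cited adult manikin trial (section 1.1).

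**Assumed input.** R², the share of depth variance explained by the baseline covariates, is not in the documents. I use 0.05 to 0.30.

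**1. Reproduce the plan's figure.** n per arm = 2(1.960 + 1.282)² × 11² / 5² = 101.7, so 102. Then 3 × 102 + 24 = 330. Both stated figures reproduce. Power at 102 per arm is 90.1% by the normal approximation and 89.8% by the noncentral t. The unadjusted plan delivers its stated power.

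**2. Effect of adjustment.** Residual SD = 11 × √(1 − R²). Power is two-sample noncentral t at 102 per arm and 5 mm. Half-width = t(0.975, 202) × residual SD × √(2/102), with t = 1.972. Equivalent n per arm = 102 / (1 − R²).

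| R² | Residual SD (mm) | Power | 95% CI half-width (mm) | Equivalent n per arm |
|---|---|---|---|---|
| 0 | 11.00 | 89.8% | 3.04 | 102 |
| 0.05 | 10.72 | 91.2% | 2.96 | 107 |
| 0.10 | 10.44 | 92.6% | 2.88 | 113 |
| 0.20 | 9.84 | 95.1% | 2.72 | 128 |
| 0.30 | 9.20 | 97.1% | 2.54 | 146 |

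**3. Cost in degrees of freedom.** The table does not charge for the covariates. With 306 participants in three arms the residual degrees of freedom are 303; five covariates leave 298. The variance penalty is about (303 − 1)/(303 − 5 − 1) = 302/297 = 1.017, or about 2%. Break-even R² = 1 − 1/1.017, about 0.02. With the charge, the half-width at R² 0.05 is 2.96 × √1.017 = 2.98 mm, so the gain remains but is small.

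**4. Would the gain pay for a multiplicity correction?** With Bonferroni over the three pairs (0.05/3 = 0.0167), at 102 per arm and 5 mm:

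| R² | Power, SD 11 | Power, SD 11.6 |
|---|---|---|
| 0 | about 80% | 74.6% |
| 0.10 | 84.2% | 79.6% |
| 0.20 | 88.7% | 84.7% |
| 0.30 | 92.8% | 89.6% |

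At SD 11, regaining 90% needs an R² a little under 0.24. At SD 11.6, even 0.30 falls just short.

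**5. Is SD 11 too small?** The equal-n pooled SD of the cited trial is √((11.6² + 10.2²)/2) = 10.9, just under the 11 used.

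**The case against.** The strongest reply is that this is a preference and not a defect. Under individual randomisation the raw difference in means is unbiased, and the t-test's standard error already allows for chance imbalance. The analysis matches the sample size calculation, which uses a marginal SD. Nothing in the protocol promises adjustment, and describing the arms is a legitimate use of demographic data. All of this stands, and it limits the point to efficiency.

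It is also fair that the size rests on an R² found nowhere in the documents. At 0.05 to 0.10 the gain is only 1.4 to 2.8 power points and 0.08 to 0.16 mm of half-width, which is small against a 5 mm target. Height and weight come from direct questioning, so some values may be missing and would need a rule.

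The reply does not show that excluding adjustment is the better choice. The loss if the covariates are uninformative is about 2% of variance; the gain if they are informative is worth 5 to 44 participants per arm with no extra recruitment.

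Three stronger readings are tempting, and the documents support none of them:
- A reader might infer that adjustment would more than pay for controlling multiplicity across three comparisons. Over most of the assumed range it does not.
- A reader might take the 11.6 in one arm of the cited trial as proof that SD 11 is optimistic. The two arms pool to about 10.9.
- A reader might conclude that randomisation is unstratified. Section 2.7.1 names no stratification factor, but it does not say there is none.

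**Conclusion.** The point holds as a missed efficiency. Section 6.2.1 bars adjustment, without giving a reason, for variables that are recorded before allocation and are plausibly prognostic for a physical-effort outcome. The planned analysis remains valid and delivers its stated 90% power.

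The quoted sentence, the timing of the data and the likely direction of the effect are secure. The size is conditional on R². It is worthwhile at 0.20 to 0.30 (power 95.1% to 97.1%), modest at 0.05 to 0.10 (91.2% to 92.6%), and nil below about 0.02. These figures take SD 11, 5 mm and 102 analysed per arm from the protocol, and assume a linear covariate effect common to the arms. Any contribution towards a multiplicity correction should be described as a partial offset only.

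**What to change.** In section 6.2.1, replace the sentence excluding adjusted analyses with wording to this effect: mean compression depth will be analysed with a linear model containing arm, age, gender, height, weight and any previous CPR training (yes/no). The model will give the three-arm F-test and adjusted pairwise mean differences with 95% confidence intervals. The unadjusted ANOVA and t-tests will be reported alongside.

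The covariate list should be fixed before any outcome data are seen, and a simple rule for missing covariate values should be stated with it.

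The cost is a short text change, with no new data to collect. Five covariates use 5 of about 300 residual degrees of freedom, about 2% of variance if they turn out not to be prognostic. The sample size need not change, because 102 per arm already supports the unadjusted comparison.

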2.2.2 Secondary objective

The secondary objectives of the trial are to assess the impact of CPR instruction terminology on other CPR quality metrics.

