2.3 Outcome measures

The outcome measures selected for this study are key CPR quality metrics that are associated with outcome in cardiac arrest. We will also record other outcomes that may influence any choice of terminology in international guidelines.

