2.3.2 Secondary efficacy outcomes

The secondary outcomes are:

- Chest compression rate (min^{-1})
- Chest compression count
- % of chest compressions in target rate range (100-120 compressions per minute)
- % of chest compressions in target depth range (50-60mm)
- % delivery of good quality CPR over two-minute study period (defined as mean CPR depth in target range (50-60mm), chest compression rate in target range (100-120 compressions per minute, and with full recoil)

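### Five secondary outcomes each get three pairwise tests and an ungated three-group test at 0.05, with no order among them and no statement that they are supportive

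*Protocol*

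**What the plan says.** Section 6.2.1 of the protocol opens its inferential plan with "For the analysis of outcomes, we will conduct two groups of analyses", without separating primary from secondary outcomes. The first group is pairwise. Its sentence reads "The first analysis will compare each of the outcomes with another outcome", but the list in brackets after it shows that the three instruction arms are meant, compared two at a time. The second group is the overall test: "The second analysis will compare all three groups, using an ANOVA test, Kruskal-Wallis test, or Chi-square test, depending on the type of data". It comes after the pairwise tests and is not described as a condition for reading them. The section closes with one threshold: "All tests will be two-tailed with a p-value cut-off for significance of 0.05".

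Section 2.3.2 lists five secondary outcomes: compression rate, compression count, percentage in the rate range, percentage in the depth range, and "delivery of good quality CPR over two-minute study period". Section 2.2.2 ties them to an objective: "The secondary objectives of the trial are to assess the impact of CPR instruction terminology on other CPR quality metrics". The protocol gives no order among the five and does not say whether they are supportive or exploratory.

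**The concern.** The secondary p-values are to be read by the same rule as the primary ones. With three arms and five outcomes, that gives many chances for at least one p-value below 0.05 when no wording affects any of these measures. The outcomes also overlap. Rate and count over about two minutes are nearly the same quantity, and the percentage in the rate range is related to both. One chance imbalance between arms could therefore appear as several findings that seem to support each other.

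What is at stake is how an isolated secondary result would be reported. Under the written rule, one significant contrast out of 15 could be described as significant on the same footing as the depth result.

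This is not simply a detail left to a statistical analysis plan. The protocol itself fixes the threshold for all tests, and a later plan that called these outcomes exploratory would have to depart from that sentence.

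**Working it through.** **The plan's own figure.** Section 6.1 gives a 5 mm difference, SD 11, two-sided alpha 0.05 and 90% power.

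n per arm = 2 × (1.960 + 1.282)² × 11² / 5² = 2 × 10.51 × 121 / 25 ≈ 101.7, rounded up to 102.

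This agrees with the stated 102 per arm, and 3 × 102 + 24 = 330. The protocol states no familywise error rate, so there is no such figure to reproduce.

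**Number of secondary tests (sections 2.3.2 and 6.2.1).**
- Pairwise: 5 × 3 = 15.
- Three-group: 5 × 1 = 5.
- Expected false-positive pairs if no wording differs on any secondary outcome: 15 × 0.05 = 0.75.

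**Error for one outcome.** In simulated null trials (three arms of 102, two-sided t-tests at 0.05), at least one of the three pairs is significant 12.2% of the time. Three independent tests would give 1 − 0.95³ = 14.3%; the figure is lower because each pair shares an arm with the others. Counting the three-group test as well leaves it at 12.2%, because a significant three-group result almost always comes with a significant pair.

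**Error over the five outcomes.** The simulation used 200,000 null trials per setting, normal outcomes and a common between-outcome correlation. The protocol gives no correlation, so the whole range is shown. The last column counts a pair only when that outcome's three-group test is also significant.

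| Assumed correlation | At least one significant pair | Same, with three-group gate |
|---|---|---|
| 0 | 48.0% | 22.7% |
| 0.3 | 44.6% | 21.1% |
| 0.5 | 39.7% | 18.8% |
| 0.7 | 32.9% | 15.3% |
| 0.9 | 23.7% | 10.7% |

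Cross-checks at correlation 0:
- Ungated: 1 − (1 − 0.1228)⁵ = 48.1%, where 0.1228 is the simulated one-outcome rate in that run.
- Gated: 1 − 0.95⁵ = 22.6%.

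**Overlap between rate and count.** If these two are treated as one outcome and the remaining outcomes as independent, there are four outcomes and the ungated figure is 40.7%. Further correlation lowers it.

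**Effect of the gate.** For a single outcome, reading the pairs only after a significant three-group test brings the error from 12.2% to 5.0%. Across the five outcomes it still leaves about 11% to 23%.

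**The case against.** The strongest reply is that the protocol already ranks its outcomes. It names one primary objective and one primary outcome, bases the sample size on depth alone, and labels the rest secondary. Nowhere does it say that a wording will be recommended on a secondary result. Unadjusted secondary outcomes are common in a low-risk manikin trial, and ordering or labelling them is often left to the statistical analysis plan. Much of this stands, and it is why the point is minor. What remains is the blanket 0.05 rule, which the protocol does state and which treats secondary tests exactly like primary ones.

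A reader might infer more than the documents support:

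- **That there is no hierarchy at all.** There is one between primary and secondary. What is missing is an order within the five and a statement of how they will be read.
- **That the chance of a false finding is a flat 40%.** That figure needs an assumed correlation of 0.5 and no true difference on any secondary outcome.
- **That it is 64%, from 1 − 0.95²⁰.** This treats all 20 tests as independent. They are not: pairs share arms, and each three-group test uses the same data as its pairs.
- **That the secondary outcomes are meant to drive guideline wording.** Section 2.3 says "We will also record other outcomes that may influence any choice of terminology in international guidelines", but it follows a sentence about CPR quality metrics. It can be read as meaning outcomes beyond those metrics, so it is too ambiguous to carry that inference.
- **That the protocol refuses multiplicity correction.** Its statement that no adjusted analyses are planned most likely concerns covariates.

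**Conclusion.** The point holds as a modest one. As written, section 6.2.1 allows any of 15 secondary contrasts to be called significant at 0.05, with no gate, no order and no supportive label. If the wordings differ on none of the five outcomes, the chance of at least one such result is about 24% to 48%, or roughly five to ten times the nominal 5%. For any one outcome it is about 12%.

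The range rests on 102 participants per arm, a common correlation between 0.9 and 0, and normal outcomes, which is an approximation for the percentage and good-quality measures. The count of tests and the single threshold come directly from the text and need no assumption.

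The same rule gives about 12% for the three depth comparisons. That is a separate and more consequential matter, and correcting it alone would leave the secondary tests unchanged.

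**What to change.** In section 6.2.1:

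1. Limit the 0.05 significance rule to the primary outcome.
2. State that the five secondary outcomes are supportive or exploratory, that they are reported as differences or odds ratios with 95% confidence intervals, and that no wording is chosen on a secondary result alone.
3. State that the pairwise comparisons for an outcome are interpreted only if its already planned three-group test is significant. This holds the error at about 5% for that one outcome. It does not control error across outcomes, which is why step 2 is needed as well.

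The cost is a few sentences, with no extra participants, data or analyses. The downside is that an isolated secondary p-value below 0.05 can no longer be presented as a confirmed effect.

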2.7 Randomisation

2.7.1 Randomisation

Participants will be individually randomised in a 1:1:1 ratio to receive one of the following terminologies:

1. Press at least 5cm
2. Press approximately 5cm
3. Push hard and fast

Participants will be randomised strictly sequentially as participants are eligible for randomisation.

An internet-based randomisation system will be used to randomly assign participants to groups. Details of how to access the service will be provided to sites in a trial specific working instruction

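### Mean compression depth gets three ungated pairwise t-tests alongside a three-group test, all at 0.05, and no rule says which decides; if the wordings are equivalent, the chance of a significant pair is about 12%

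*Protocol*

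**What the plan says.** The trial has three arms and one primary outcome, mean chest compression depth (protocol 2.3.1). On allocation, section 2.7.1 says: "Participants will be individually randomised in a 1:1:1 ratio to receive one of the following terminologies".

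Section 6.2.1 sets out two groups of analyses for the outcomes. The first takes each wording against each other wording, giving three pairs. For continuous data each pair has a mean difference, a 95% confidence interval and a t-test p-value. On the second, it says: "The second analysis will compare all three groups, using an ANOVA test, Kruskal-Wallis test, or Chi-square test, depending on the type of data". One threshold covers everything: "All tests will be two-tailed with a p-value cut-off for significance of 0.05". The section does not name a leading pair, make the pairwise tests conditional on the three-group result, or say which analysis settles the primary objective.

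Section 6.1 sizes the trial: "We require 102 participants in each study arm to reliably detect a 5 mm difference in chest compression depth between groups with 90% power", at a "significance level of 0.05" and with an SD of 11. It then adds an allowance for loss: "We have included an additional 24 participants to account for drop-outs and data loss". This gives 306 + 24 = 330 in total, or 110 per arm.

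**The concern.** The three pairs address one question on one outcome: does the wording of the instruction change depth? If any significant pair can be read as a yes, there are three chances of a false yes, each at 5%. The ANOVA on the same data is a single 5% test of the same question, but the plan neither ranks it above the pairs nor below them.

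Two things are at stake. The first is the false-positive risk on the primary outcome when the wordings do not differ. The second is a result with one pair below 0.05 and a non-significant ANOVA. The protocol gives no basis for saying whether such a trial has shown an effect, and the choice would be made after seeing the data. Section 2.3 has guideline terminology in view as a use of the results, so the rule is worth settling beforehand.

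**Working it through.** **Inputs.** Difference 5 mm, SD 11 mm, 90% power, alpha 0.05 and 102 per arm (6.1); two-sided tests (6.2.1); three equal arms (2.7.1).

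**1. The plan's own figure.** For one two-group comparison, n = 2(z₀.₉₇₅ + z₀.₉₀)²σ²/δ² = 2 × (1.960 + 1.282)² × 121/25 = 101.7, so 102. This is an exact match (a t-based version gives 102.7). Power at 102: the standard error is 11 × √(2/102) = 1.540, 5/1.540 = 3.246, and Φ(3.246 − 1.960) = 0.901. The 90% is therefore the power of one unadjusted pair at 0.05.

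**2. Error of three ungated pairs, all wordings equivalent.** The pairs share arms, so the tests are correlated. At least one pair is significant when the range of the three means exceeds 1.96 × √2 = 2.772 standard errors of a mean. The studentized range distribution for three groups gives 12.2%. One million simulated trials give 12.2% at 102 and at 110 per arm. Treating the tests as independent would give 1 − 0.95³ = 14.3%, which is too high.

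**3. Does the ANOVA add to it?** No. With equal arms and a pooled variance, F is the average of the three squared pairwise t statistics. It cannot exceed two-thirds of the largest. A significant F (above about 3.03 on 2 and 303 df) therefore needs a largest t² of at least 1.5 × 3.03 = 4.5, well past the pairwise cut-off of 1.968² = 3.87. In the simulation, which used ordinary two-sample t-tests, the ANOVA was never significant without a significant pair. Its own rate was 5.0%.

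**4. One wording differs and the other two are equal.** Only one pair is then truly null, so the error is 5%.

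**5. Disagreement between the two analyses.** With equal means it is 12.2% − 5.0% = 7.2% of trials. With means 0/2.5/5 mm, simulation gives about 8%. By step 3 it always runs one way: a significant pair with a non-significant ANOVA.

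**6. With the ANOVA as a gate.** For three arms, a significant ANOVA followed by pairwise tests at 0.05 is a closed procedure. Simulated family-wise error under equal means is 5.0%.

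**7. Power with the gate.** ANOVA noncentrality is nΣ(μᵢ − μ̄)²/σ².

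- Means 0/2.5/5: 102 × 12.5/121 = 10.54, ANOVA power 83.2%.
- Means 0/0/5: 102 × 16.67/121 = 14.05, ANOVA power 92.6%.

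Power for a 5 mm pair when the ANOVA must also be significant (simulated):

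| Per arm | Means 0/2.5/5 | Means 0/0/5 |
|---|---|---|
| 102 | about 82% | about 88% |
| 110 | about 86% | about 90% |

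For comparison, Bonferroni at 0.05/3 = 0.0167 per pair gives about 80% at 102 per arm and 83% at 110. Restoring 90% would need 131 per arm, or 3 × 131 = 393 before losses.

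**The case against.** The strongest reply is that the plan is silent rather than wrong. A gated procedure would still test everything at 0.05, so the threshold sentence would remain true, and a statistical analysis plan could supply the order. Part of this stands: the remedy is a clarification. But the protocol does more than leave a gap. It lists the pairwise tests first, each with its own p-value and threshold, and the three-group test second. Followed as written, the pairs stand alone.

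It can also be argued that separate pairwise questions in a multi-arm trial need no correction, that all pairs and the three-group test will be reported so readers see the whole family, and that this is a low-risk manikin study. These points bear on severity. They do not tell the trial team what to conclude when the two analyses differ.

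Four stronger readings are tempting, and the document does not support them:

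- A reader might infer that the protocol promises a 5% family-wise rate and breaks it. It states only a per-test level.
- A reader might infer that the sample size is wrong. It is correct for one unadjusted pair, which is a legitimate basis when pairwise comparisons are listed first.
- A reader might count every test across the secondary outcomes as further inflation. Those outcomes are labelled secondary, and a count alone gives no error rate.
- A reader might assume that covariate adjustment would win back the lost power. Section 6.2.1 rules out adjusted analyses, and the protocol gives no correlation between any covariate and depth.

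**Conclusion.** The point holds as a should-fix. For the primary outcome the protocol sets three ungated pairwise tests beside a three-group test and gives no deciding rule. The chance of at least one significant pair is about 12% if all three wordings are equivalent. It is not a general error rate for the trial: with one wording different and two equal, it is 5%. The conflict between analyses, about 7-8% of trials, is for equal means or means of 0/2.5/5 mm at 102 per arm.

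These figures assume equal arms, approximately normal mean depths and a common SD. The 12% and 5% error rates do not depend on the value of the SD, but the power figures rest on the protocol's SD of 11. The Kruskal-Wallis route was not simulated; there the three-group test might add slightly to the error.

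**What to change.** In 6.2.1, for mean depth, state that the three arms are compared first by ANOVA at two-sided 0.05. The pairwise t-tests at 0.05 are then confirmatory only if that test is significant. Otherwise the pairwise differences and intervals are still reported, but descriptively. If the normality check leads to Kruskal-Wallis, use it as the gate for matching rank-based pairwise tests, so that gate and pairs address the same kind of hypothesis.

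In 6.1, keep 102 per arm and 330 in total. Say that 90% is the power of one unadjusted pair, and add the gated figures: about 82-88% for a 5 mm pair at 102 per arm, and 86-90% if all 110 per arm give data.

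The cost is a few sentences and no extra participants. The downside is stated power about 2 to 8 points below 90% at 102 per arm, and at most about 4 points below with complete data. At 102 per arm this still exceeds Bonferroni's 80%.
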